**1.1 Research Background** 

# 1.1.1 Basic Overview

Acute Respiratory Distress Syndrome (ARDS) often complicated with Right Ventricular Dysfunction (RVD), the incidence of which can be as high as 64%. Acute cor pulmonale is the most serious form of ARDS complicated with RVD.The mechanisms include pulmonary vascular dysfunction and right ventricular systolic dysfunction.Excessive inflammation, hypoxic pulmonary vasoconstriction, hypercapnia, elevated pulmonary vascular resistance due to hyperventilation or pulmonary collapse, pulmonary capillary microthrombosis and pulmonary vascular remodeling are important factors leading to right heart dysfunction in ARDS.RVD often leads to low cardiac displacement and hemodynamic failure in patients.ARDS patients with RVD have a worse prognosis and a significantly higher risk of death, which is an independent risk factor for death in ARDS patients.

Mechanical ventilation is an important treatment for moderate/ severe ARDS.Mechanical ventilation has a significant effect on hemodynamics by affecting the right ventricle by increasing intrathoracic positive pressure.On the one hand, periodic (moist respiration) or continuous (PEEP application) changes in transpulmonary pressure caused by respiratory support directly affect the right ventricular outflow impedance.On the other hand, increased intrathoracic pressure caused by respiratory support directly affect the right ventricular outflow impedance.On the other hand, increased intrathoracic pressure caused by respiratory support can limit right ventricular diastole.In addition, during mechanical ventilation, alveolar pressure will directly act on the outside of pulmonary capillary bed. If alveolar pressure exceeds venous pressure, pulmonary blood flow will be obstructed.Therefore, mechanical ventilation may significantly increase the right cardiac afterload by increasing intrathoracic or alveolar pressure, resulting in right cardiac dysfunction and hemodynamic disorders.

APRV is an inversely proportional mechanical ventilation mode with transient pressure release under continuous positive airway pressure.

Studies have shown that APRV can improve oxygenation and is very safe compared with lung protective ventilation with low tidal volume [6]. It is worth noting that randomized controlled studies have shown that APRV can increase average airway pressure compared with low tidal volume ventilation [7], which may theoretically increase intrathoracic and alveolar pressure, increase external pericardium pressure, thereby affecting venous return, increasing pulmonary circulation resistance, and leading to right heart dysfunction and even hemodynamic deterioration.However, the actual effect of APRV on right heart function in ARDS patients has not been reported.In this study, transthoracic cardiac ultrasound was used to evaluate right heart function, pulmonary artery pressure, tricuspid regurgitation and hemodynamics related indicators in ARDS patients receiving APRV mechanical ventilation, so as to fully understand the influence of APRV mechanical ventilation mode on right heart function and hemodynamics, which is more conducive to clinical application and avoid the occurrence of adverse reactions.

#### **1.1.2 Research Types**

Prospective single-center observational study

#### 1.1.3 Research Basis

ARDS is often complicated with RVD, and the incidence can be as high as 64%. ARDS patients with RVD have a worse prognosis and a significantly higher risk of death, which is an independent risk factor for death in ARDS patients. Randomized controlled studies have shown that compared with low tidal volume ventilation, APRV can increase average airway pressure [7], which may theoretically increase intrathoracic pressure and extrapericardial pressure, thereby affecting venous return, increasing pulmonary circulation resistance, leading to right heart dysfunction and even hemodynamic deterioration. However, the actual effect of APRV on right heart function in ARDS patients has not been reported.

# 1.2 Risk/benefit assessment

#### 1.2.1 Known potential risks

Several animal and clinical studies have confirmed that APRV can effectively improve oxygenation and reduce the duration of mechanical

ventilation compared with traditional mechanical ventilation mode, and the clinical application of APRV is somewhat safe. Therefore, there is no potential risk in this study.

# **1.2.2 Probability of injury**

Mechanical ventilation is the most important and necessary treatment for patients with respiratory failure, and its safety has been proven.Mechanical ventilation does far more good than harm when compared to severe life-threatening respiratory failure.

#### 1.2.3 Degree of injury

The subjects suffered very minor injuries and had no fatal adverse events.

#### 1.2.4 Known potential benefits

ARDS is an acute, diffuse, inflammatory lung injury that results in increased alveolar capillary permeability, lung weight gain, and loss of aerated lung tissue.Mechanical ventilation is the primary treatment for ARDS patients.APRV ventilation can effectively improve oxygenation in ARDS patients and reduce the duration of mechanical ventilation, which is very safe compared to other mechanical ventilation modes.

#### 1.2.5 Assessment of potential risks/benefits

Mechanical ventilation is the main treatment for ARDS patients. APRV mechanical ventilation is a mode of mechanical ventilation that has been used in the treatment of ARDS patients for more than 20 years. Animal and clinical studies have shown that APRV mechanical ventilation can safely and effectively improve oxygenation, reduce the duration of mechanical ventilation and ICU stay, which can benefit ARDS patients. The potential risks of APRV are similar to those of other mechanical ventilation modes. With indications and contraindications, APRV has little risk and is a life-saving treatment for patients with ARDS.

#### **1.3 Discussion**

Acute Respiratory Distress Syndrome (ARDS) often complicated with Right Ventricular Dysfunction (RVD), and the incidence of RVD was as high as 64%.RVD often leads to low cardiac displacement and hemodynamic failure in patients.ARDS patients with RVD have a worse prognosis and a significantly higher risk of death, which is an independent risk factor for death in ARDS patients.

Mechanical ventilation is an important treatment for ARDS patients.Mechanical ventilation has a significant effect on hemodynamics by influencing right ventricular function through intrathoracic positive pressure, especially in patients with existing right ventricular insufficiency.

APRV is an inversely proportional mechanical ventilation mode with transient pressure release under continuous positive airway pressure (CPAP). APRV is commonly used in the treatment of ARDS patients. APRV improves oxygenation and is safe compared to low tidal volume lung protective ventilation and SIMV, but randomized controlled studies have not shown that APRV improves mortality. It is not clear whether the reason is related to APRV increasing average airway pressure [7], thus increasing pulmonary circulation resistance, leading to right heart dysfunction, or even hemodynamic deterioration. However, the actual effect of APRV on right heart function in ARDS patients has not been reported. In this study, transthoracic cardiac ultrasound was used to evaluate right heart function, pulmonary artery pressure, tricuspid regurgitation and hemodynamics related indicators in ARDS patients receiving APRV mechanical ventilation, so as to fully understand the influence of APRV mechanical ventilation mode on right heart function and hemodynamics, which is more conducive to clinical application and avoid the occurrence of adverse reactions.

#### 2. Study Objective/end point

**Objective**: To study the effect of APRV on right ventricular function in ARDS patients.

**Primary endpoint/outcome**: Effect of APRV mechanical ventilation for 24 hours on right heart function in ARDS patients.

**Secondary end point/outcome**: Effects of APRV ventilation at 6h, 12h, 48h, 72h and 24h after APRV ventilation on right heart function in ARDS patients.

Effects of APRV ventilation at 6h, 12h, 24h, 48h, 72h and 24h after APRV ventilation on hemodynamics of ARDS patients.

Mortality rate of ARDS patients on APRV mechanical ventilation at 28 days after enrollment, length of stay in ICU, length of stay, and mortality rate in hospital.

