# 3.Study design

# 3.1 Overall Design

(1). A single center prospective observational study.

(2).In ARDS patients receiving APRV mechanical ventilation, right heart function was monitored at 6, 12, 24, 48, 72 hours after APRV mechanical ventilation, and 24 hours after APRV mechanical ventilation. Mechanical ventilation parameters, respiratory mechanics and arterial blood gas analysis were recorded, and hemodynamic indexes were recorded at the same time.

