# 3.3 Sample size

This study is to study the effect of APRV on right heart function. Referring to previous literatures, the number of subjects is generally required to be 40, and the number of subjects should be increased to 50 in consideration of shedding and withdrawal, etc.

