#### 8. Statistical analysis and statistical methods

Prism 4.01 was used for statistical analysis software.Because all the parameters are non-normally distributed, the data is represented as the median (quartile range;Head).Friedman ANOVA of repeated measurements was used to compare the data obtained at each step and, where appropriate, through Dunn post hoc tests using Bonferroni correction.Qualitative data were compared with Fisher's exact test.All comparisons were double-tailed, with P<0.05 indicating the existence of significant differences.

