# 9.2 Medical treatment and protection of subjects during the study

The rights and welfare of the subjects will be protected during the study, and the quality of their medical care will not be affected by their refusal to participate or withdrawal from the study.

If the patient drops out of the study, we will no longer conduct study related tests.

The investigator will provide insurance for the subjects participating in the study program. If the subjects suffer any damage related to the study, they will receive timely and free treatment and be compensated or compensated according to laws and regulations and mutual agreements.

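### The 24 h primary endpoint has no rule for patients who die or come off APRV before 24 h, and the protocol's other provisions tend to lose their data

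*Protocol*

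**What the plan says.** - **Endpoint.** Section 2 of the protocol gives the primary endpoint as "Effect of APRV mechanical ventilation for 24 hours on right heart function in ARDS patients"; Section 6.1 repeats it. Neither has a rule for death or the end of APRV before 24 h.
- **Population and schedule.** Section 3.1: "In ARDS patients receiving APRV mechanical ventilation, right heart function was monitored at 6, 12, 24, 48, 72 hours after APRV mechanical ventilation". Section 5 adds a scan before APRV. A further scan follows 24 h after APRV, which makes seven occasions.
- **Dropout.** Section 9.2: "If the patient drops out of the study, we will no longer conduct study related tests". The protocol does not say whether a patient whose APRV is stopped or changed has dropped out.
- **Losses.** Section 3.3 states that "the number of subjects is generally required to be 40" and that "the number of subjects should be increased to 50 in consideration of shedding and withdrawal, etc". It gives no loss rate and no breakdown by cause.
- **Analysis.** Section 8: "Friedman ANOVA of repeated measurements was used to compare the data obtained at each step", with Dunn post hoc tests under Bonferroni correction and two-sided testing at 0.05.
- **The harm under study.** Section 1.1.1 fears that raised airway pressure may end by "leading to right heart dysfunction and even hemodynamic deterioration". Sections 1.1.1 and 1.3 also say that right ventricular dysfunction often brings hemodynamic failure and carries a higher risk of death.
- **Deaths.** Section 2 counts them in 28-day and in-hospital mortality, which are secondary outcomes.

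**The concern.** The outcome that the study looks for can itself remove the 24 h value. A patient whose right heart fails on APRV may die, or be taken off APRV, before the 24 h scan. Take a patient who comes off APRV at 10 h. Scans exist before APRV and at 6 h. The protocol does not say whether a 24 h scan is due, or whether a scan taken 14 h after APRV stopped would count as the 24 h value. The post-APRV scan falls at 10 + 24 = 34 h, when a pressure effect may have gone.

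If such patients have no usable 24 h value, the primary result describes those who tolerated APRV, while the objective concerns ARDS patients given APRV. Enrolling 50 instead of 40 restores the number of patients but does not remove the selection.

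**Working it through.** **1. The plan's own figure.** Required number divided by (1 - loss): 40/(1 - 0.20) = 50. The total fits a 20% loss over the whole study, a rate that the protocol never states. The 40 cannot be reproduced, because no effect size, SD or power is given.

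**2. Inputs that must be assumed.** The protocol gives no rate of death or stopping of APRV by 24 h, so I take 4%, 10% and 20% (2, 5 and 10 of 50). It gives no effect size, so I take a normally distributed change with a true median of -0.5 SD, negative meaning worse.

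**3. Extreme bound: exactly the worst fraction q is lost.** The completers' median is then the percentile q + (1 - q)/2 of the full distribution.
- q = 4%: 52nd percentile, z = 0.050, median -0.45 SD
- q = 10%: 55th percentile, z = 0.126, median -0.37 SD
- q = 20%: 60th percentile, z = 0.253, median -0.25 SD

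**4. Partly informative loss (simulation).** Loss falls on the fraction q with the lowest value of a latent score that correlates with the change. A correlation of +0.5 means that worsening patients tend to be lost; -0.5 means that improving patients leave early.

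| Loss | Median, correlation +0.5 | Shift | Median, correlation -0.5 |
|---|---|---|---|
| 4% | -0.46 | 0.04 towards zero | -0.54 |
| 10% | -0.41 | 0.09 towards zero | -0.59 |
| 20% | -0.33 | 0.17 towards zero | -0.66 |

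**5. Power.** A two-sided signed-rank test at 0.05 stands in for the before-versus-24 h comparison. With all 50 patients, power is about 92%. Among completers it is:
- loss unrelated to the change: about 90%, 90% and 85% at 4%, 10% and 20% loss
- loss correlated 0.5 with worsening: about 87%, 78% and 56%

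The gap between the two rows is the part that extra enrolment does not repair.

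**6. Bounds on a proportion.** Suppose about 20% of completers worsen. Counting none, then all, of the lost patients as worsened gives the range for all 50.
- 2 lost: 10/48 = 20.8%; range 10/50 = 20% to 12/50 = 24%
- 5 lost: 9/45 = 20%; range 9/50 = 18% to 14/50 = 28%
- 10 lost: 8/40 = 20%; range 8/50 = 16% to 18/50 = 36%

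**7. The stated test.** The Friedman test in standard form ranks each patient's values across occasions and needs a value at every one. If one test spans all seven occasions, a patient with a 24 h scan but no 72 h or post-APRV scan is also removed. That selection is stricter than reaching 24 h.

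**8. A worst-rank primary as the remedy.** With no true change, n = 50 and a signed-rank test, giving the worst rank to 2, 5 or 10 patients chosen without regard to the right heart produces about 6%, 18% and just over 60% false positives. In a cohort without a comparator this could charge unrelated deaths to APRV.

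**The case against.** A reader might infer that the primary endpoint counts only patients who complete 24 h of APRV. No section says so. Section 3.1 describes patients receiving APRV, scanned at set times, and defines no completers' set. The dropout sentence in 9.2 follows one about refusal and withdrawal, so it can be read as covering withdrawal alone. On that reading a patient who is off APRV but still enrolled could be scanned at 24 h. Section 3.3 names neither death nor stopping APRV. This objection stands: the defect is a missing rule, not a stated exclusion.

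Analysis sets and missing data are commonly left to a SAP, and Section 10.5.1 refers to a statistical analysis proposal and to defining the analysis group before database lock. That stands for the analysis, but not for data collection. A SAP cannot recover a scan that was never taken. The data lists in Sections 3.2 and 5 do not name the reason APRV ended.

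Early harm is partly captured elsewhere: by the 6 h and 12 h scans, the hemodynamic indices, mortality and serious adverse event reports. That is true, but none of these enters the primary result.

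The exclusions in Section 4.3 (refractory shock, severe cardiac dysfunction, expected ventilation under 48 h) should keep early loss low. This also stands, and it makes the 4% row more plausible than the 20% row, though the protocol gives no rate to settle it.

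**Conclusion.** The point holds as a gap in the endpoint definition and in follow-up. The protocol ties its primary endpoint to 24 h of APRV and has no rule for patients who do not get there. Its dropout, sample size and test provisions, followed as written, tend to lose them. Loss caused by right heart or hemodynamic failure would move the result towards no harm.

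Two stronger readings are not supported. The first is that the overall bias must favour APRV: patients may also leave APRV early because they improve, which shifts the result by a similar amount the other way. The second is that half of any deterioration would vanish: that needs a 20% loss before 24 h made up of exactly the worst 20%, whereas the 20% is only implied, for the whole study and for all causes.

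The size is therefore unknown. Illustratively it is 0.04, 0.09 and 0.17 SD at 4%, 10% and 20% loss, on an assumed true median of -0.5 SD and an assumed correlation of 0.5 between loss and worsening. The case for acting is that the remedy is cheap and cannot be applied after the data are collected.

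**What to change.** 1. In Section 9.2, state that a patient whose APRV is stopped or changed stays in the study with scans continuing, and that only withdrawal of consent ends testing.
2. Where APRV ends before 24 h, bring the 24 h scan forward to the time of stopping where feasible, and use it as the last on-APRV value.
3. Add to the CRF the time and reason APRV ended.
4. In Sections 2 and 8, make the primary comparison pre-APRV versus 24 h in all patients who start APRV and have a baseline scan, so that a missing 48 h, 72 h or post-APRV scan does not remove anyone.
5. Report the number and reasons of early deaths and stops beside the 24 h result.
6. Use a worst-rank analysis, limited to death or stopping for right heart or hemodynamic deterioration, only as a sensitivity analysis.

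The cost is protocol wording, one CRF field, a little more analysis and some scans at a non-nominal time. No patients are added, and no rule on when APRV is stopped is changed.

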# 3.Study design

# 3.1 Overall Design

(1). A single center prospective observational study.

(2).In ARDS patients receiving APRV mechanical ventilation, right heart function was monitored at 6, 12, 24, 48, 72 hours after APRV mechanical ventilation, and 24 hours after APRV mechanical ventilation. Mechanical ventilation parameters, respiratory mechanics and arterial blood gas analysis were recorded, and hemodynamic indexes were recorded at the same time.

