# **3.2** Collect the following data:

(1) Demography: sex, age, height, weight

(2) Vital signs: SOFA score and APACHE II score were measured 24 hours after admission to ICU and randomness.

(3) Physiological and biochemical indexes: blood routine, blood biochemistry (total protein, ALB, total bilirubin, AST, ALT, GGT, blood urea nitrogen, serum creatinine), TNI, BNP, CRP before APRV, APRV24h, 48h, 72h and at the end of APRV24h.
(4)Respiratory mechanical parameters before APRV, APRV6h, 12h, 24h, 48h, 72h

and end APRV24h.

(5)Cardiac ultrasound and hemodynamic indexes before, after, and after APRV at 6, 12, 24, 48, 72, and 24h.

(6)Fatality rate at 28 days after inclusion, length of stay in ICU, length of stay, and

fatality rate in hospital.

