# 4.3 Exclusion criteria

- (1). Younger than 18 years old or older than 80 years old
- (2). BMI of obese patients  $\geq$  35kg/m2;
- (3). Pregnant and lactating women
- (4). The expected time of invasive mechanical ventilation is less than 48h
- (5). Neuromuscular diseases known to require prolonged mechanical ventilation
- (6). Severe chronic obstructive pulmonary disease
- (7). Intracranial hypertension

(8). Pulmonary bullae or pneumothorax, subcutaneous emphysema, mediastinum emphysema

(9). ECMO treatment was performed when admitted to ICU

(10). Refractory shock

(11). Severe cardiac dysfunction (New York Heart Association Class iii or iv, acute coronary syndrome or persistent ventricular tachyarrhythmia), enlargement of the right heart due to chronic cardiopulmonary disease, cardiogenic shock or major cardiac surgery;

(12). Informed consent was not signed

Note: All subjects meeting either of the exclusion criteria at baseline will be excluded from the study

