# 5. The items and frequency of clinical and laboratory examinations to be performed

Cardiac ultrasound examination was performed before APRV mechanical ventilation, 6h, 12h, 24h, 48h, 72h after APRV mechanical ventilation, and 24h after APRV mechanical ventilation. Mechanical ventilation parameters were recorded, respiratory mechanics and arterial blood gas analysis were measured, and hemodynamic indexes were recorded.

Collect the following data:

(1). Demography: sex, age, height, weight

(2). Vital signs: 24h SOFA score and APACHE II score after admission to ICU and randomization

(3). Physiological and biochemical indicators: echocardiographic right heart function monitoring, hemodynamic parameters and arterial blood gas were performed before APRV or LTV mechanical ventilation, 6h, 12h, 24h, 48h, 72h after mechanical ventilation, and 24h after mechanical ventilation.

(4). Blood routine examinations, blood biochemistry (total protein, ALB, total bilirubin, AST, ALT, GGT, blood urea nitrogen, serum creatinine), TNI, BNP and CRP were performed at 24, 48 and 72 hours after admission to ICU and randomization.

()Respiratory mechanical parameters before and after randomization at 24h, 48h and 72h.

Case fatality rate at 28 days after inclusion, length of stay in ICU, length of stay, and in-hospital case fatality rate.

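### Scans timed from the start of APRV and one timed from its end share the same wording and endpoint label, so 48 h and 72 h results may include off-APRV scans and a missing post-APRV scan can remove a patient from the 24 h comparison

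*Protocol*

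**What the plan says.** Four places describe the schedule, and they do not use one clock.

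- **Section 3.1:** "right heart function was monitored at 6, 12, 24, 48, 72 hours after APRV mechanical ventilation, and 24 hours after APRV mechanical ventilation". The same phrase covers both 24 h points; the second is given only as "and 24 hours after APRV mechanical ventilation".
- **Section 3.2, laboratory item:** "CRP before APRV, APRV24h, 48h, 72h and at the end of APRV24h". This wording shows that the second 24 h point is counted from the end of APRV.
- **Section 3.2, ultrasound item:** "Cardiac ultrasound and hemodynamic indexes before, after, and after APRV at 6, 12, 24, 48, 72, and 24h". The figure 24 appears twice in one list with no anchor.
- **Section 5, item 3:** "before APRV or LTV mechanical ventilation, 6h, 12h, 24h, 48h, 72h after mechanical ventilation, and 24h after mechanical ventilation". Here the clock is tied to mechanical ventilation, not to APRV.

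Section 2 names right heart function after 24 h of APRV as the primary endpoint. It then lists as secondary "Effects of APRV ventilation at 6h, 12h, 48h, 72h and 24h after APRV ventilation on right heart function", so on-treatment and post-treatment points carry one label.

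Section 8 says "Friedman ANOVA of repeated measurements was used to compare the data obtained at each step", followed where appropriate by Dunn tests with Bonferroni correction. It names no separate test for the 24 h change. No section fixes how long APRV lasts. The nearest criterion, in section 4.3, excludes patients for whom "The expected time of invasive mechanical ventilation is less than 48h".

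**The concern.** The study asks whether the higher airway pressure of APRV harms the right heart. A scan taken after APRV has stopped cannot show an on-APRV effect at that time. If such scans are counted in the 48 h and 72 h results, a real on-APRV change looks smaller, and the result could be read as reassurance.

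The second risk is loss of patients. Friedman ranks each patient across all steps, so every step must be present. A patient who dies on APRV after the 24 h scan, or who misses the post-APRV scan for another reason, has the data for the primary time point but would drop out of the test that contains it. Such losses are unlikely to be random with respect to right heart function.

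**Working it through.** **1. The protocol's own figure.** Section 3.3 gives 40 subjects, raised to 50 for losses. The 40 cannot be reproduced, because no effect size, SD or power is stated. The step to 50 fits an unstated 20% loss: 40 / (1 − 0.20) = 50.

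**2. Timing.** If APRV lasts T hours, the post-APRV scan falls at T + 24 h, and every fixed scan later than T is off APRV.

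| T (h) | Post-APRV scan (h) | Fixed scans taken off APRV |
|---|---|---|
| 24 | 48 | 48 h, 72 h |
| 36 | 60 | 48 h, 72 h |
| 48 | 72 | 72 h |
| 60 | 84 | 72 h |
| 72 | 96 | none |
| 120 | 144 | none |

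**3. Share off APRV.** The document gives no durations. For illustration, assume lognormal durations with log-SD 0.6, so that f(t) = Φ[(ln t − ln median) / 0.6].

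| Assumed median (h) | Off at 48 h | Off at 72 h |
|---|---|---|
| 48 | 50% | 75% |
| 72 | 25% | 50% |
| 96 | 12% | 32% |
| 120 | 6% | 20% |

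**4. Dilution.** Assume the effect is absent once APRV stops. The expected change in all patients scanned is then (1 − f) × on-APRV change:

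- f = 20%: 0.80 of the effect
- f = 40%: 0.60
- f = 60%: 0.40

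**5. What dilution does to the 72 h comparison.** This was simulated with 40 patients, 7 steps (7 × 6 / 2 = 21 Dunn pairs) and 1,500 runs. The assumed effect was 0.8 within-patient SD on APRV and 0 off it.

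| Off at 48 h / 72 h | Expected 72 h shift (SD) | Power, 72 h v baseline |
|---|---|---|
| 0 / 0 | 0.80 | about 54% |
| 10% / 25% | 0.8 × 0.75 = 0.60 | about 22% |
| 20% / 40% | 0.8 × 0.60 = 0.48 | about 12% |
| 30% / 60% | 0.8 × 0.40 = 0.32 | about 3% |

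The last row also let one scan serve as both a fixed and a post-APRV scan; at 20% / 40%, doing so made almost no difference. The overall Friedman test rejected in 98–99% of runs throughout, so the loss lies in the 72 h comparison, not in the overall test.

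**6. Complete series.** If a share m of 50 patients has no post-APRV scan, a seven-step test keeps 50 × (1 − m): 45 at m = 10%, 40 at 20% and 30 at 40%. These values of m are assumptions. At 20% this one scan uses up the whole allowance for losses, even if every 24 h scan was obtained.

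**The case against.** The strongest reply is that section 8 never lists the steps, and a SAP that is not shown may do so. That stands: placing the post-APRV scan inside the Friedman test is a reading of the text, though the plain one. The mixed anchors and the shared endpoint label are the protocol's own wording and need correcting in any case.

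A second reply is that section 3.1 concerns patients receiving APRV, so someone already off APRV may simply have no 72 h value. Nothing would then be mislabelled. But that patient would be missing a step, and a complete-series test that includes 72 h would drop the patient altogether. The change proposed below covers both readings.

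It is also fair that a post-treatment scan at a variable time is legitimate. Friedman ranks conditions within a patient and needs no common clock time.

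A reader might infer four stronger things, which the documents do not support:

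- **That one scan counted twice distorts the test.** Exact coincidence needs APRV to stop at 24 h or 48 h. In simulation with no effect, the Friedman test rejected in 3.8–5.5% of runs, duplicated scans included.
- **That off-APRV scans reverse the effect.** The factor (1 − f) shrinks a change towards zero and never alters its sign.
- **That the 48 h exclusion criterion makes early stops certain.** It concerns expected total invasive ventilation, not APRV. Early stops are possible; their frequency is unknown.
- **That the primary time point is contaminated.** The 24 h scan is off APRV only if APRV stops before 24 h.

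**Conclusion.** The point holds in two parts. First, the time points have mixed anchors under one label, and the 48 h and 72 h results may blend on-APRV and off-APRV scans. The apparent change is then 80%, 60% or 40% of the on-APRV change for assumed off-APRV shares of 20%, 40% or 60%, provided the effect disappears on stopping. Second, on the plain reading of section 8, the 24 h comparison depends on each patient also having a post-APRV scan. The first part affects secondary results. The second reaches the primary comparison through lost and selected patients, not through a faulty 24 h scan. The durations, shares and effect sizes are all assumptions, because the protocol gives none. The point merits a change to the text and does not undermine the study.

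**What to change.** 1. **Sections 2, 3.1, 3.2 and 5:** state for each time point whether it is counted from the start or the end of APRV, and reconcile the four descriptions.
2. **Section 8:** limit the Friedman steps to baseline, 6, 12 and 24 h. This leaves 4 × 3 / 2 = 6 Dunn pairs instead of 21.
3. **Sections 2 and 8:** take the post-APRV scan out of that test. Analyse it as its own paired contrast with the last on-APRV scan and with baseline, and report APRV duration.
4. **Sections 2 and 8:** analyse 48 h and 72 h as paired contrasts with baseline, both in all patients scanned and in those still on APRV at the scan. Give the number on APRV, and note that this subset is selected by who remains on APRV. On-APRV-only values should not become Friedman steps, because early stoppers would then drop out of the 24 h comparison.
5. **Section 3:** record APRV status at each scan. The protocol records ventilation parameters but does not name the mode.

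No extra scan and no clinical rule is needed. The cost is one recorded item, a little more analysis, and smaller, selected numbers for the on-APRV results at 48 h and 72 h.
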